5.4.2.2. Summary of PPK and PK/PD Modeling

cut.

The primary efficacy consideration for initial dose selection in this study was the development of PPK and PK/PD models using data from Studies 101 and 201.

PD endpoints in these models included AP Wieslab in healthy and PNH subjects, lactose dehydrogenase (LDH) in subjects with PNH naïve to C5 inhibitors, and C3 opsonization in PNH subjects with inadequate response to ongoing C5 inhibitor therapy. AP Wieslab was used as a real-time marker of overall complement activation. LDH was used as a marker of intravascular hemolysis (IVH, terminal complement inhibition) and C3 opsonization was used as a marker of the potential for extravascular hemolysis (EVH, proximal complement inhibition). Target occupancy of Factor D is not expected to be affected by a terminal complement inhibitor,

allowing for models of IVH and EVH to be extrapolated to all subjects with PNH regardless of C5 inhibitor status.

Separate PK/PD models were constructed for AP Wieslab, LDH, and C3 opsonization of RBCs. Overall, the models performed well and were able to describe trends in the observed data.

The LDH model in C5 inhibitor-naïve PNH subjects was characterized by indirect inhibition,

Outcomes of PK/PD modeling are summarized in Figure 2 (comparison of predicted inhibitory concentrations with PPK-predicted C_{tau}).

Figure 2: Comparison of PK/PD Model-Estimated IC Values (95% CI) for AP Wieslab, LDH, and C3 Opsonization in Subjects with PNH with Median (10th to 90th percentile) PPK Model-Estimated C_{tau} at 200, 400, and 500 mg BID

Abbreviations: AP = alternative pathway; BID = twice daily; CI = confidence interval; IC = inhibitory concentration; LDH = lactate dehydrogenase PK/PD = pharmacokinetic/pharmacodynamic; PPK = population pharmacokinetic(s).

Notes: Each simulation assumes perfect adherence and optimal spacing of BID doses (ie, every 12 hours).

5.5. Benefit-Risk Analysis

Subjects may derive a benefit in improving surrogate clinical markers of disease progression (eg, reducing proteinuria) and controlling the symptoms of their disease with BCX9930. Study subject selection criteria, dose selection, assessment of clinical benefit at Week 24, and study monitoring assessments have been designed to maximize the potential benefit-risk ratio of BCX9930 in subjects with C3G, IgAN, and PMN.

Regular monitoring of safety parameters, including AEs, laboratory assessments, vital signs, ECGs, and physical examination findings, will be mandated to ensure that the benefit-risk profile supports continued dosing.

The DMC will regularly review the cumulative safety data from this study, as well as the accumulating, long-term safety data across all BCX9930 studies in all indications per Section 13.7. Subject data may be reviewed by a Nephrology Risk Mitigation Working Group (NRMWG) for additional recommendations, including dose reduction, interruption of dosing, and permanent discontinuation.

It is anticipated that BCX9930 will continue to be made available in each country until such time as BCX9930 either receives commercial approval or until BioCryst discontinues development of the product, whichever comes first.

Potential risks associated with complement inhibitors for the treatment of C3G, IgAN, and PMN as well as potential risks associated with BCX9930 based on nonclinical and clinical data to date are described in the IB for BCX9930 and are summarized below.

5.5.1. Potential Risks of Bacterial Infections

The most significant risk associated with complement inhibitor therapies, including the approved therapies eculizumab or ravulizumab, is the risk of life-threatening or fatal meningococcal infections (Figueroa and Densen 1991, Hillmen, Young et al. 2006). This risk is well known and included as a warning in relevant labels for both Soliris® (eculizumab) and Ultomiris® (ravulizumab) (Alexion Pharmaceuticals 2020, Alexion Pharmaceuticals 2021).

As BCX9930 blocks the AP of complement, subjects may have increased susceptibility to bacterial infections, especially infections with encapsulated organisms, such as *Neisseria meningitidis*, *Streptococcus pneumoniae*, and *Haemophilus influenzae*, but also with unencapsulated strains of *Neisseria meningitidis* and other bacteria such as *Neisseria gonorrhoeae* (Ram, Lewis et al. 2010). Study subjects receiving BCX9930 will be monitored closely for signs and symptoms of infection, and infection risk will be mitigated by requiring subjects to have up-to-date vaccinations against appropriate bacterial strains. If required on an individual basis, prophylactic antibiotic administration will be allowed.

5.5.2. Potential Risk of SARS-CoV-2 Infection and Vaccination

Complement inhibitors do not inhibit cellular or humoral immunity. Therefore, BCX9930 is not expected to increase the risk of contracting coronavirus disease (COVID-19) following infection with the severe acute respiratory syndrome coronavirus 2 (SARS-CoV-2) or to increase the risk of severe illness with COVID-19.

All study activity will be conducted in accordance with relevant local, regional, and national guidance around COVID-19. In order to minimize the risk of COVID-19 transmission, additional procedures or assessments (which may include but are not limited to symptom assessment, temperature, viral ribonucleic acid [RNA] testing, and antibody testing) may be implemented at the discretion of the investigator and sponsor medical monitor beyond those required for this protocol.

Vaccination against SARS-CoV-2, the causal agent for COVID-19 infection, is allowed, if authorized and available in country or area, and based on investigator's judgment.

The sponsor's current risk assessment, relative to COVID-19 vaccination in clinical trials with BCX9930, is that authorized or available COVID-19 vaccinations are unlikely to have any potential interaction or added safety risk, if given in combination with ongoing investigational product BCX9930. While there is a known or expected higher risk of certain bacterial infections in patients treated with complement inhibition (including with BCX9930 treatment), or in patients with certain hereditary complement deficiencies, there is no clear known increased or compounded risk with vaccinations (such as currently authorized COVID-19 vaccinations) in the setting of complement inhibition. Also, currently there is no theoretical concern or data to

suggest that complement inhibition with ongoing BCX9930 treatment would impact potential efficacy of vaccinations against SARS-CoV-2.

5.5.3. Potential Risks of Adverse Events with BCX9930

5.5.3.1. Potential Risks for Headache

In Study 101, early-onset headache was the most common TEAE in subjects with PNH treated with BCX9930, likely consistent with restoration of nitric oxide homeostasis due to improved control of intravascular hemolysis with BCX9930. This is likely to be a PNH-specific event and is usually mild and transient.

[figure not shown]
5.5.3.2. Potential Risks for Drug Rash

A benign maculopapular rash with consistent onset and clinical course has been observed with multiple-day dosing of BCX9930 in both healthy volunteers and subjects with PNH. Clinical experience to date indicates that this rash occurs early in treatment, persists for approximately 5 to 8 days, and resolves while continuing dosing of BCX9930.

5.5.3.3. Potential Risks for Hepatic Effects

Toxicities identified in nonclinical studies and detailed in the IB for BCX9930 are monitorable with standard blood and urine clinical chemistry tests. Serum chemistries, including liver transaminases, bilirubin, and alkaline phosphatase (ALP), will be followed closely in this study to monitor for any hepatocellular and biliary system changes. Hepatic synthetic function will be monitored by prothrombin time, international normalized ratio (INR), albumin, and total protein levels in blood. The additional laboratory measurements performed through the first 12 weeks of BCX9930 treatment include monitoring for hepatic toxicities.

5.5.3.4. Potential Risks for Renal Effects

Monitoring of renal function will be undertaken in the study using standard measures (eg, sCr, eGFR, and urinalysis including microscopy, and safety biomarker analysis) Further information can be found in Section 12.11.5.

, the frequency of laboratory assessments has been increased to monitor for any changes in renal function. Any kidney-related events occurring on study should be evaluated as detailed in Section 13.5.2.

5.5.4. Risks of Potential Adverse Events with Trial-Mandated Procedures

Outpatient percutaneous needle biopsies of the kidney will be conducted during the study in accordance with the schedule of assessments and local practice and guidelines. The risk of complications, such as major bleeding, is low (< 1%) for outpatients with proteinuric kidney disease and preserved kidney function with normal hematologic parameters (Koirala and Jefferson 2020).

To reduce the risk of complications from the biopsy procedure and to minimize the total number of study-related biopsy procedures conducted during screening, study subject selection criteria exclude patients with a higher risk of complications, and the screening biopsy will be performed only after all other study eligibility criteria are met for each subject. In addition, the screening biopsy may be waived with the approval of the central pathologist and agreement of the medical monitor for any subject with a recent biopsy as specified in section 7.1.

5.5.5. Overall Benefit-Risk Analysis

The development of BCX9930 may be of benefit to patients with complement-mediated diseases, including those with C3G, IgAN, or PMN, that are clinically important and associated with chronic morbidity and that are potentially life-threatening.

dose level. Based on the sponsor's preliminary investigations, reducing the BCX9930 dose to 400 mg BID and introducing a step-up regimen (ie, starting dosing at 200 mg BID for 2 weeks before escalating to 400 mg BID) is anticipated to mitigate the risk of renal injury while maintaining the potential for demonstrating clinical benefit in the subjects with C3G, IgAN, or PMN. Study subject eligibility criteria, dose selection, staggered enrollment of subjects with an eGFR of ≥ 30 mL/min/1.73 m², as well as more frequent study monitoring assessments have been included to optimize benefit and to minimize the risk of toxicities to study participants. Regular monitoring of safety parameters, including AEs, clinical laboratory abnormalities, vital signs measurements, ECGs, and physical examination findings, will ensure that the benefit-risk profile supports continued dosing. In addition, an independent, program-wide DMC, whose membership includes a nephrologist, will regularly review the cumulative safety data from this study, as well as the accumulating, long-term safety data across all BCX9930 studies in all indications. The overall benefit-risk balance is, therefore, considered to be acceptable for this study.

6. STUDY OBJECTIVES AND PURPOSE

6.1. Objectives

The objectives in this POC study of orally administered BCX9930 are applicable to the 3 parallel treatment cohorts of subjects with C3G, IgAN, or PMN.

6.1.1. Primary Objective

The primary objective of this study is:

To evaluate the therapeutic potential of BCX9930 as assessed by proteinuria

6.1.2. Secondary Objectives

The secondary objectives of this study are:

- To evaluate the safety and tolerability of BCX9930
- To evaluate the therapeutic potential of BCX9930 as assessed by other measures of clinical benefit
- To evaluate effects of BCX9930 on kidney biopsy morphologic findings (C3G cohort only)

6.1.3. Exploratory Objectives

The exploratory objectives of this study are:

6.2. Endpoints

The endpoints in this POC study of orally administered BCX9930 are applicable to the 3 parallel treatment cohorts of subjects with C3G, IgAN, or PMN.

6.2.1. Primary Endpoints

The primary endpoint of this study is:

• Change in 24-hour urinary protein excretion normalized to urine creatinine as measured by percentage change in uPCR from baseline

[figure not shown]
6.2.2. Secondary Endpoints

The secondary endpoints of this study are:

- Number and proportion of subjects with a uPCR response defined as:
 - Partial remission, $\geq 50\%$ reduction from baseline
 - Complete remission, $\leq 500 \text{ mg/g}$
 - Normalization, $\leq 200 \text{ mg/g}$
- Change from baseline in 24-hour urinary protein excretion as measured by percentage change in urinary protein from baseline
- Change from baseline in eGFR
- Change from baseline in serum albumin
- Number and proportion of subjects with the following parameters:
 - Protein \geq 3.5 g in a 24-hour urine collection
 - Serum albumin $\leq 2.5 \text{ g/dL}$
- Number and proportion of subjects with a morphologic response in each of the following categories (C3G cohort only at Week 24):
 - Decreased endocapillary hypercellularity, mesangial hypercellularity, active crescents (if present), glomerular leukocyte infiltration, fibrinoid necrosis, membranoproliferative glomerulonephritis pattern
 - Decreased acute tubular injury, interstitial inflammation, interstitial edema
 - Reduction in C3 glomerular staining
 - Reduction in the extent of deposits, clearing of deposits, or no additional active deposits as assessed by electron microscopy (EM)
 - No progression of chronic changes (ie, global, segmental glomerulosclerosis, tubular atrophy/interstitial fibrosis, arteriosclerosis)
- Number and proportion of subjects with a TEAE
- Number and proportion of subjects who discontinue due to a TEAE
- Number and proportion of subjects who experience a treatment-emergent serious adverse event (TESAE)
- Number and proportion of subjects who experience a Grade 3 or 4 TEAE based on Common Terminology Criteria for Adverse Events (CTCAE)
- Number and proportion of subjects who experience a CTCAE treatment-emergent Grade 3 or 4 laboratory abnormality

6.2.3. Exploratory Endpoints

The exploratory endpoints of this study are:

7. INVESTIGATIONAL PLAN

7.1. Overall Study Design

This is a Phase 2, open-label, multicenter, POC study to evaluate the safety, tolerability, and therapeutic potential of BCX9930, an oral Factor D inhibitor, administered for up to 52 weeks in adult (≥ 18 years old) subjects with either C3G, IgAN, or PMN. After up to a 56-day screening

qualification period, approximately 14 eligible subjects will be enrolled into each of 3 parallel study treatment cohorts and will receive BCX9930 200 mg BID for the first 14 days and will increase to BCX9930 400 mg BID on Day 15 for the remainder of the treatment period.

During the study, recruitment into each of the cohorts will be managed independently with a total of approximately 42 subjects enrolled into the study. For the C3G cohort only, up to 7 subjects with at least 6 months of treatment with a stable dosing regimen of mycophenolate mofetil or mycophenolate sodium prior to the Day 1 Visit will be allowed to enroll in the study per Section 8.2. Sites will be notified when enrollment is complete for subjects with C3G receiving mycophenolate mofetil/mycophenolate sodium.

After providing written informed consent to participate in the study and confirming that all other study eligibility criteria have been met during screening, subjects will undergo a percutaneous needle biopsy of the kidney per local practice and guidelines. Renal biopsy images and details from the local pathology report will be reviewed by the central pathologist for confirmation of a protocol-defined diagnosis of C3G, IgAN, or PMN. The screening biopsy procedure may be waived with approval of the central pathologist and agreement with the medical monitor for any subject who has undergone a renal biopsy procedure as follows: within 3 months prior to screening for the C3G cohort, within 6 months prior to screening for the IgAN or PMN cohorts, provided that required materials are adequate for pathology evaluation per protocol procedures.

After the Day 1 Visit, subjects will be required to return to the clinic at Weeks 1, 2, and 4, and then every 4 weeks thereafter through Week 24. Additional safety assessments will be performed at Weeks 3, 5, 6, 7, and 10, either at the investigative site, or at a local laboratory more convenient for the subject or via a home health service (where permitted and available). At the Week 24 Visit, the clinical benefit of BCX9930 treatment will be assessed by the investigator. Subjects who are assessed as deriving clinical benefit will continue treatment up to Week 52. described in Table 2 and Table 3.

An on-treatment, percutaneous needle biopsy of the kidney will be performed at the following visit after completion of all other assessments, or during the time specified below by treatment cohort:

- Week 24 or within 7 days after the visit for subjects with C3G
- Week 36 or within 7 days after the visit for subjects with IgAN (optional)
- Week 48 to within 3 days after the Week 52 Visit for subjects with PMN (optional)

The on-treatment biopsy is optional for subjects with IgAN or PMN. For subjects with PMN, if the biopsy is scheduled after the Week 52 Visit, then dosing with BCX9930 will continue until the day of the biopsy procedure. WSIs of LMs, digital IFs or IHCs, digital EMs, and details from the local pathology reports from the on-treatment biopsies will be reviewed by the central pathologist. Protocol-specified, on-treatment biopsies will not be required for subjects who are discontinued from BCX9930 treatment.

Subjects who complete BCX9930 dosing through Week 52 and who are discontinued from BCX9930 dosing prior to Week 52 will return to the clinic approximately 4 weeks (28 ± 3 days) after the date of their last dose of BCX9930 for the Safety Follow-up (FU) Visit prior to study completion/discontinuation.

[figure not shown]
A study schema is shown in Figure 3.

An optional serial PK/PD substudy will include subjects who provide consent from each of the 3 cohorts to evaluate the PK and PD of BCX9930 at the Day 1 Visit and/or at a subsequent visit prior to the Week 24 Visit. Serial sampling of urine and blood will be performed over a period of 6 hours. Subjects who do not participate in the Baseline (Day 1) PK/PD sample collection are eligible to participate at a subsequent clinic visit prior to the Week 24 Visit.

All subjects will have a single blood sample drawn for PK analysis at each clinic visit ("sparse sampling" to support PPK and PK/PD modeling). For subjects participating in the serial PK/PD substudy, a single blood sample will be drawn for PK and PD analysis at visits where serial blood samples are not collected through 6 hours post dose.

All subjects who sign a separate informed consent (optional) will participate in exploratory pharmacogenomics testing at a single visit from Day 1 up to the Week 24 Visit (including the safety FU Visit, if applicable).

Figure 3: Study Schema

 ⁼ Kidney Biopsies: A screening biopsy may be waived with approval of central pathologist and agreement with the medical monitor for any subject
who has undergone a renal biopsy procedure as follows: within 3 months prior to screening for the C3G cohort, within 6 months
prior to screening for the IgAN or PMN cohorts.
 Subjects with C3G will undergo a percutaneous needle biopsy of the kidney at the Week 24 Visit or within 7 days after the visit.

Note: Subjects will return to the clinic at Weeks 1, 2, and 4, and then every 4 weeks thereafter through Week 52. Additional safety assessments will be performed at Weeks 3, 5, 6, 7, and 10, either at the investigative site or at a laboratory local to the subject or via a home health service.

Additional visits may occur during the study and are not represented (eg, additional screening visits, unscheduled visits, or visits for biopsy procedures)

7.2. Number of Subjects

This study will enroll approximately 14 adult subjects in each of the C3G, IgAN and PMN cohorts for a total enrollment of approximately 42 subjects.

7.3. Treatment Assignment

All eligible subjects will receive BCX9930 200 mg BID for the first 14 days and will increase to BCX9930 400 mg BID on Day 15 for the remainder of the treatment period; doses should be taken approximately 12 hours apart. The first dose of BCX9930 will be administered at the Day 1 Visit after completion of all baseline procedures and under supervision of clinic staff.

7.4. Individual and Study Termination Criteria

7.4.1. Study Drug Treatment Discontinuation Criteria

A subject will be permanently withdrawn from BCX9930 for any of the following reasons:

• Pregnancy in a female subject.

^{† =} Clinical Benefit Assessment

T = Safety Follow-up Visit: 28 ± 3 days after last dose of BCX9930 for all subjects

F = Safety Follow-Up

- Emergence of an AE, including a laboratory abnormality, or other unacceptable toxicity that, in the judgment of the investigator, compromises the ability of the subject to continue study-specific procedures or it is considered not to be in the subject's best interest to continue due to an altered benefit-risk profile.
- Intercurrent illness or the emergence of a new medical condition that would, in the judgment of the investigator, affect assessments of clinical status to a significant degree.
- Treatment-emergent alanine aminotransferase (ALT) or aspartate aminotransferase (AST) > 3 × ULN combined with either laboratory abnormalities indicative of significant hepatic toxicity (ie, meeting Hy's law, total bilirubin > 2 × ULN OR with an INR > 1.5) or with symptomatology of acute hepatitis (ie, severe fatigue, nausea, vomiting, right upper quadrant pain and tenderness, fever, rash, and/or eosinophilia [> 5%]) and assessed by the investigator as probably, or definitely related to BCX9930 treatment.
- Treatment-emergent increase in sCr \geq 3 × ULN (confirmed by repeat testing) without any other potential cause of renal dysfunction
- In the investigator's opinion it is in the best interest of the subject to discontinue from further dosing.
- Invasive meningococcal infection or any serious invasive bacterial infection that occurs after BCX9930 is initiated.
- Subject request to discontinue for any reason.
- Subject noncompliance (eg, protocol deviation), as assessed by the sponsor or investigator, to be detrimental to study or subject benefit-risk profile.
- Discontinuation at the request of the sponsor, relevant competent authority, or the governing institutional review board (IRB), research ethics board (REB), or independent ethics committee (IEC) (collectively referred to as "ethics committee").

Whenever possible, the investigator will consult with the sponsor medical monitor (or designee) before discontinuing study treatment. The reason for discontinuation of study treatment will be recorded in the source documents and electronic case report form (eCRF). Subjects who are discontinued from BCX9930 dosing prior to Week 52 will return to the clinical site approximately 4 weeks $(28 \pm 3 \text{ days})$ after the date of their last dose for a safety FU Visit prior to discontinuation from the study.

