13.3. Relationship to Study Drug

An investigator who is qualified in medicine must make the determination of relationship to the investigational product for each AE (not related, unlikely related, possibly related, probably related, definitely related). The investigator should decide whether, in his or her medical judgment, there is a reasonable possibility that the event may have been caused by the investigational product. If no valid reason exists for suggesting a relationship, then the AE should be classified as "not related." If there is any valid reason, even if undetermined, for

^{*}Instrumental ADL refer to preparing meals, shopping for groceries or clothes, using the telephone, managing money, etc.

^{**}Self-care ADL refer to bathing, dressing and undressing, feeding self, using the toilet, taking medications, and not bedridden.

^{***} Grade 5 (Death) is not appropriate for some AEs and therefore is not an option.

suspecting a possible cause-and-effect relationship between the investigational product and the occurrence of the AE, then the AE should be considered "related."

Not Related: The event can be readily explained by other factors such as the subject's

> underlying medical condition, concomitant therapy, or accident, and no temporal relationship exists between the study drug/IMP and the event.

Unlikely The event does not follow a reasonable temporal sequence from drug

Related: administration and is readily explained by the subject's clinical state or by

other modes of therapy administered to the subject.

There is some temporal relationship between the event and the administration **Possibly** Related:

of the study drug/IMP and the event is unlikely to be explained by the subject's

medical condition, other therapies, or accident.

The event follows a reasonable temporal sequence from study drug/IMP **Probably**

Related: administration, abates upon discontinuation of the study drug/IMP, and cannot

be reasonably explained by the known characteristics of the subject's clinical

state.

Definitely The event follows a reasonable temporal sequence from study drug/IMP

administration, follows a known or suspected response pattern to the study Related:

drug/IMP, is confirmed by improvement upon stopping the study drug/IMP

(dechallenge), and reappears upon repeated exposure (rechallenge, if

rechallenge is medically appropriate).

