13.5.1. Potential Drug-induced Liver Injury: Monitoring, Evaluation, and Discontinuation Criteria

All treatment-emergent ALT elevations $> 3 \times \text{ULN}$ should be confirmed, preferably within 72 hours, with repeat assessment of ALT, AST, total bilirubin, ALP, prothrombin time/INR, and complete blood count with differential. These may be repeated at a local laboratory as long as the results are reported to the investigator when available and the investigative site contacts the subject to ascertain any symptoms.

Subjects with potential drug-induced liver injury (pDILI) meeting this ALT elevation must be assessed to determine whether study drug must be withheld or discontinued per Sections 7.4.1. In addition, any potentially contributing medications, supplements, or over-the-counter medications that are not medically necessary should be discontinued if medically feasible.

Discontinuation of treatment should be considered for any of the following, and should be discussed with the sponsor medical monitor, considering the benefit: risk of discontinuing BCX9930:

[figure not shown]
- ALT or AST $> 8 \times ULN$
- ALT or AST > 5 \times ULN for more than 2 weeks

- ALT or AST > 3 × ULN and total bilirubin > 2 × ULN (unless there is evidence that
 the increase in bilirubin is due to Gilbert's syndrome) or INR > 1.5 in the absence of
 warfarin therapy
- ALT or AST > 3 × ULN with the appearance of fatigue (over baseline fatigue), nausea, vomiting, right upper quadrant pain or tenderness, fever, rash, and/or eosinophilia (> 5%)

If subjects are asymptomatic with no other pertinent laboratory abnormality, study drug may be continued under close observation. Transaminases, total bilirubin, ALP, and INR should be repeated at least twice weekly. Frequency of retesting can decrease to once per week or less if abnormalities stabilize or the study drug has been discontinued and the subject is asymptomatic. Additionally, several other items should be considered, including obtaining a more detailed history of symptoms and prior or concurrent diseases; obtaining a history of concomitant use of nonprescriptive medications, herbal and dietary supplements, alcohol intake, recreational drug use, special diets; evaluation for acute viral hepatitis A, B, C, D, and E and potentially other serologies; evaluation for others as clinically indicated including alcoholic and autoimmune hepatitis, non-alcoholic steatohepatitis (NASH), and biliary tract disease.

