If Hy's Law criterion is met and assessed as probably or definitely related to study drug by the investigator, then study drug must be discontinued per treatment discontinuation criterion in Section 7.4.1. The investigator should contact the sponsor medical monitor for a discussion regarding the event and assessment. If medically indicated, the investigator can discontinue the subject immediately and follow up with the sponsor within 24 hours.

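### The mandatory liver withdrawal rule needs a 'probably' or 'definitely' related rating, and both ratings are defined by what happens after the drug is stopped; no visible text expressly requires the stop

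*Protocol*

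**What the plan says.** Protocol 7.4.1 lists the reasons for which a subject is permanently withdrawn from BCX9930. The liver entry needs ALT or AST > 3 × ULN, together with either a laboratory sign of significant hepatic toxicity (Hy's Law, with total bilirubin > 2 × ULN, or INR > 1.5) or symptoms of acute hepatitis. It also needs the event to be "assessed by the investigator as probably, or definitely related to BCX9930 treatment". Section 13.5.1 says the same of Hy's Law: if the criterion is met and "assessed as probably or definitely related to study drug by the investigator, then study drug must be discontinued".

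Section 13.3 defines the two grades. 'Probably' combines a reasonable time sequence with an event that "abates upon discontinuation of the study drug/IMP, and cannot" be reasonably explained by the subject's clinical state. 'Definitely' requires, among other things, that the event "is confirmed by improvement upon stopping the study drug/IMP", and that it recurs on re-exposure if "rechallenge is medically appropriate".

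For ALT > 3 × ULN, 13.5.1 says that subjects "must be assessed to determine whether study drug must be withheld or discontinued per Sections 7.4.1". It then gives a second, softer tier: "Discontinuation of treatment should be considered for any of the following, and should be discussed with the sponsor medical monitor". That list has four entries and no causality condition.

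**The concern.** A stopping rule for liver injury should work at the moment the laboratory result arrives, when the subject is normally still taking the drug. Here the rule depends on a rating whose definition looks back at what happened after the drug was stopped. At first assessment there has been no dechallenge. An investigator who applies 13.3 literally can go no higher than 'possibly', and 'possibly' does not trigger withdrawal.

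The subjects at stake are those with transaminase elevation plus raised bilirubin, raised INR or hepatitis symptoms, and no likely alternative cause. They are the ones a Hy's Law rule exists to protect. Potential drug-induced liver injury is an event of special monitoring in 13.1.4, and hepatic laboratory monitoring was intensified over the first 12 weeks (5.5.3.3, 11.3.5).

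**Working it through.** No arithmetic beyond counting applies, and the plan gives no figure to reproduce. The check sets the sections side by side.

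**1. Which grades trigger the rule, and can each be assigned during uninterrupted dosing?** Grades are from 13.3; triggers are from 7.4.1 and 13.5.1.

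| Grade | Needs an outcome after stopping? | Triggers mandatory withdrawal? |
|---|---|---|
| Not related | No | No |
| Unlikely | No | No |
| Possibly | No | No |
| Probably | Yes (abatement) | Yes |
| Definitely | Yes (improvement) | Yes |

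Five grades; 2 trigger; both of those need an after-stopping outcome. Of the 3 grades that can be assigned without stopping, 0 trigger. The conditions within each triggering definition are cumulative, so the dechallenge element is not optional. The wording about medical appropriateness in 'definitely' attaches to rechallenge only.

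**2. Where does a typical case fall before dechallenge?** 'Possibly' covers an event with some time relation to dosing that other causes are unlikely to explain. A new Hy's Law picture with no evident alternative cause fits that description, so it falls one grade below the trigger.

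**3. Does any visible text require the prior stop?**

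- 13.5.1, mandatory assessment: it requires a decision on withholding or discontinuing and points back to 7.4.1, which contains no hold rule.
- 13.5.1, second tier: discontinuation is to be considered and discussed with the medical monitor.
- 13.5.1, continuation: allowed under close observation for asymptomatic subjects with no other pertinent laboratory abnormality. This implies that drug is not continued in the cases at issue, but does not say so.
- 13.5.1, Hy's Law paragraph: the investigator should contact the medical monitor and may stop at once if medically indicated.
- 10.3.1: interruption is permitted.
- 7.4.1, other entries: an AE or laboratory abnormality that alters benefit-risk, the subject's best interest, and sponsor request. The first two turn on the investigator's judgment and the third on the sponsor's decision.

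None of these expressly requires a hold at the 7.4.1 liver thresholds.

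**4. How close is the second tier to the mandatory tier?** Two of its four entries resemble the two 7.4.1 combinations, but they are not identical. The symptom entry reads "with the appearance of fatigue (over baseline fatigue), nausea, vomiting, right upper quadrant pain or tenderness, fever, rash, and/or eosinophilia"; 7.4.1 asks for severe fatigue, and for pain together with tenderness. The bilirubin and INR entry makes exceptions for Gilbert's syndrome and warfarin that 7.4.1 does not make.

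**5. Contrast within 7.4.1.** The serum creatinine entry (≥ 3 × ULN) asks for confirmation by repeat testing and the absence of another potential cause. It needs no graded rating and no dechallenge, so it can be met while dosing continues.

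**The case against.** The best defence is that the sections form a sequence. Section 7.4.1 governs permanent withdrawal. Section 13.5.1 requires assessment, 10.3.1 permits interruption, improvement then supports 'probably', and permanent withdrawal follows. No liver passage authorises continued dosing in the disputed combinations. The sponsor may also upgrade causality (13.3) or request discontinuation (7.4.1), and ALT > 3 × ULN prompts repeat testing, preferably within 72 hours. Section 13.3 asks for medical judgment about reasonable possibility, so an investigator might rate 'probably' without dechallenge.

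Most of this stands as mitigation. It does not close the gap, because the hold on which the sequence depends is permitted or implied and never required. Rating 'probably' without dechallenge departs from the grade's written definition. A sponsor upgrade does not by itself satisfy a condition tied to the investigator's assessment.

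Three stronger readings are tempting, and the documents do not support them:

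- *Subjects would be kept on drug.* Several routes to stopping exist at any time. The gap is in the mandatory rule, not in the power to stop.
- *The causality grade alone separates mandatory withdrawal from mere consideration.* The clinical thresholds also differ, as step 4 shows, so some subjects are in the softer tier on clinical grounds.
- *The two-grade condition contradicts the three-grade 'related' set in 13.3, 13.4 and SAP Section 10.* Those uses concern expedited reporting, follow-up and tabulation. A stopping rule may legitimately set a different bar.

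**Conclusion.** The point holds as a flaw in how the rule is built and should be fixed. As written, the mandatory liver criterion cannot be met during uninterrupted dosing: 0 of its 2 triggering grades can be assigned, and no visible text expressly requires the stop that would make them assignable.

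This rests on three readings. The 13.3 definitions are applied as worded. The relatedness condition in 7.4.1 governs the laboratory limb as well as the symptom limb, which 13.5.1 confirms for Hy's Law. The visible text is complete on this point; a figure is missing just before the second-tier list in 13.5.1, and the cross-reference there is plural but gives one section number, so some caution is due.

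The frequency of harm cannot be estimated from the documents. The practical effect is limited to the protocol text and any reuse of the rule: the SAP reports that development stopped in December 2022 with 2 treated subjects.

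**What to change.** Choose one of two edits. They are not equivalent.

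(a) In the liver entry of 7.4.1 and the Hy's Law sentence of 13.5.1, change the condition to *possibly, probably, or definitely related*. Cost: one word in each of two sentences. This is a change of policy, since it mandates permanent withdrawal at 'possibly'; expect a few more permanent withdrawals for events later judged unrelated.

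(b) Keep the two-grade rule and add to 13.5.1: *BCX9930 must be held when ALT or AST > 3 × ULN occurs with total bilirubin > 2 × ULN, INR > 1.5 or symptoms of acute hepatitis, and must not be restarted until the response to stopping and alternative causes have been evaluated and causality has been rated.* Cost: one sentence, and some temporary holds for unrelated events. The hold must run through evaluation of dechallenge. If it ended at the first causality rating, it could lapse the same day with 'possibly' and leave the rule unmet.

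Option (a) makes the rule usable at once. Option (b) preserves the existing work-up and makes the assess, hold, withdraw sequence explicit. Neither needs new data or analysis.
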